#### Exclusion criteria

Subjects will be excluded if they have other serious medical or psychiatric disorders or if they have a codependence on other substances such as alcohol or benzodiazepines. Patients who test positive for benzodiazepines will be excluded. They will also be excluded if they are suicidal or homicidal. Women will be excluded from entering the study if they are pregnant.

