#### **BACKGROUND AND RATIONALE**

Results of a retrospective study in adults going through opioid withdrawals suggest that the BRIDGE device can decrease symptoms of opioid withdrawal by over 87% within the first hour of treatment without the use of supportive medication. Pre-clinical studies in rats suggest that neurostimulation with the BRIDGE decreases neuronal activity in the central amygdala (2). The amygdala is a common central link between a state of chronic pain and opioid dependence. As this central nervous system structure is involved in pain processing activation it has been associated with fear and the negative emotional state of withdrawal from opioids and drug craving (3-5). It is therefore likely that the BRIDGE device will impact pain and symptoms associated with opioid withdrawal. It is well known that there is a high prevalence of pain in persons with OUD during acute opioid withdrawal. A recent study concluded that in many cases, pain is a major reason for patients opting out of treatment (6). Another study demonstrated that up to 37.5 % of patients drop out of therapy within the first month and the majority of those occur during the first week (7.8). Early dropout is often the result of severe and dysphoric symptoms of withdrawal. Thus, alleviating signs and symptoms of withdrawal effectively and rapidly at the initial time of engagement is likely to increase the likelihood of success of any treatment protocol. The first few hours and days of therapy are critical to get patients engaged thus willing to enter into secondary therapy with pharmacotherapy and counseling to prevent relapse. In a recent study, 29% of patients who were randomized to receive MAT with opioid antagonists dropped out of treatment and did not receive the first dose of medication (9).

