#### **DESIGN AND METHODS**

The study will recruit a total of 50 subjects and will take place in a well-established outpatient treatment center (Brightview). Brightview is a private addiction treatment center located in Cincinnati, Ohio. The site PI at Brightview will be [name] [name] (MD, ABIM, ABAM DABPM), a board-certified physician in addiction medicine. [name] (PhD) will be a Co-investigator. The volume of patients treated for opioid use disorder (OUD) at this facility is sufficient for patient recruitment in this study. [name] will be responsible for patient recruitment and overseeing the entire project at Brightview. He will monitor the health of all patients in the study per standard clinical practice. [name] will be responsible for patient recruitment as well and monitor protocol adherence as well as supervise data collection, entry, and analysis.

This study will involve a double-blind, randomized, controlled trial with active BRIDGE or sham device (Figure 3). The sham device will be identical in appearance to the active device but will have no electrical current. Both providers and patients will be blinded to treatment allocation throughout the study. Participants will be 18 years or older who speak English and meet criteria for opioid use disorder based on the Diagnostic and Statistical Manual of Mental Disorders-5. Patients going through acute opioid withdrawal will be assessed for the severity of opioid withdrawal using the Clinical Opioid Withdrawal Scale (COWS). Additional demographic data will be collected at presentation including age, sex, duration of opioid misuse, types of medications or illicit drugs used as well as the presence of other medical conditions. After the severity of opioid withdrawal is established (COWS score  $\geq 10$ ), subjects will be randomized in blinded fashion. Once the patient is consented, a visual analog scale (VAS) for pain and an opioid craving scale (OCS) will be completed. Baseline cognitive function will be measured with the Stroop test using the CNS Vital Signs (CNSVS) in-office neurocognitive testing software https://www.cnsvs.com/index.html. This instrument measures executive function. The test takes approximately

4 minutes to administer and will be performed at the same intervals as COWS score, pain and craving assessments before and after device placement.

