Participants in this study will be males and females between the ages of 18 and 60 years who are English speaking and capable of giving informed consent. Applicants must fulfill the criteria for opioid use disorder based upon the Structured Clinical Interview for DSM-5 (SCID). In addition, they must have an opioid (morphine, 6MAM, oxycodone or metabolites, hydrocodone or metabolites or fentanyl or metabolites, methadone or metabolites) positive urine immunoassay test during the screening process and have evidence of opioid withdrawal with COWS score  $\geq 10$ . They must be healthy, with no significant medical illnesses (e.g., insulin dependent diabetes), and without significant psychiatric illness (e.g., schizophrenia) other than their drug dependence.

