#### **Data Collected**

All data collected will be entered into a Redcap database for analysis. All collected data will be de-identified and samples will only have a unique identifier that will link the unique identifier with the patient's name.

Results of the COWS and pain VAS scores, OCS and CNSVS assessments at the respective time points will be tabulated and analyzed.

Upon completion of each patient's treatment with the device (sham or active), patients will be asked if they thought they had an active or inactive device. They will also be asked to respond to the questions: Do you want an active, functioning device to be placed prior to going home today (yes/no)? and on a 7 point Likert scale: 1) "How useful do you think the BRIDGE Device was for you overall in your treatment?" 2) "What is your impression of the effectiveness of the BRIDGE Device to treat your symptoms of withdrawal?" 3) "How satisfied are you and how the BRIDGE device worked for you?" and 4) "How likely are you to use the device again if you have symptoms of withdrawal?" Results will be tabulated and analyzed descriptively.

Analysis will also include differences in dosing of buprenorphine as well as usage of other symptom control medications and continued engagement in recovery treatment at 5- and 30-days post-device placement. If subject does not return to clinic at the 5- and 30-day scheduled appointment as dictated by clinic standard practice, a phone call will be made to assess whether the patient is still engaged in a recovery program.

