#### Safety Monitoring Plan

All procedures will be performed by trained professionals within the standard of care under continuous medical supervision while in the outpatient clinic. Potential side effects will be documented as noted above. COWS score ratings will be filled out by nursing staff or provider as per standard of care. All patients will be carefully monitored. If any serious harm or discomfort is identified by the subjects or the study personnel, the treatment will be discontinued. Any patient with worsening or no improvement in symptoms who has a device placed during the study will be able to drop out at any time and receive standard of care medical therapy. The skin of the external ear will be carefully monitored for signs of irritation or infection. All patients will be given the option to have an active device at the end of the 5 day study period at no cost.

Safety Analysis Plan

There are no dangerous interventions related to this study.

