#### NSS-2 BRIDGE placement details:

- 1. A research coordinator will document the patient ID, name and the device serial number in the study database.
- 2. The research coordinator or provider will record baseline answers to questionnaires and will also record vital signs (temperature, heart rate and blood pressure).
- 3. The neurostimulator placement will be performed as directed and per BRIDGE training protocol instructions identical to prior IRB approved protocols.

- 4. Before device placement, the subject caretakers should be advised that some discomfort is normal at first. If the discomfort persists or worsens after a few minutes the medical provider will be notified. The patients will be advised that they may feel a slight pulsing sensation and perhaps a warming sensation in the ear to which the electrodes are affixed. The pulsing and warming sensation may disappear after approximately 5 minutes. If the discomfort level increases the offending array can be repositioned until the patient's discomfort level decreases to an acceptable level.
- 5. Subjects will be advised not to immerse the device in water as the device is water resistant but not water proof. If showering or washing their hair, placing a dry wash cloth over the area to help protect the device will be recommended. Subjects will be given a contact person (Principal investigator, Co-investigator or Research coordinator) to call if they are having any problems with the device or if it falls off.
- 6. The device may be removed by the patient or a caretaker if at home. If uncomfortable doing so or unable to carry out the instructions, an outpatient appointment will be made and the device will be removed by the investigators.
- 7. If removed at home, the patient will be asked to return the used device for proper disposal when they return the following week.

#### Figure 5

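### The eligibility criteria do not exclude patients who have already worn a BRIDGE or similar ear stimulator, nor expressly bar a second randomisation (minor; a cheap improvement)

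*Combined protocol and SAP*

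**What the plan says.** The inclusion paragraph, just before Exclusion criteria, begins "Participants in this study will be males and females between the ages of 18 and 60 years who are English speaking". It goes on to require opioid use disorder on structured interview, an opioid-positive urine test, a COWS of at least 10 and otherwise good health. Exclusion criteria begins "Subjects will be excluded if they have other serious medical or psychiatric disorders or if they have a codependence on other substances" and then adds a positive benzodiazepine test, suicidality or homicidality, and pregnancy. Neither refers to earlier use of the device or earlier participation.

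Four other statements bear on this:

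- Study Purpose and Safety Analysis both describe the device as FDA-cleared.
- Design and Methods says of the control: "The sham device will be identical in appearance to the active device but will have no electrical current".
- NSS-2 BRIDGE placement details, step 4, says: "The patients will be advised that they may feel a slight pulsing sensation and perhaps a warming sensation in the ear". It adds that the sensation may be gone after about five minutes.
- Safety Monitoring Plan says: "All patients will be given the option to have an active device at the end of the 5 day study period at no cost". Data Collected has each patient asked, on completing treatment, whether they want one, and also asks "How likely are you to use the device again if you have symptoms of withdrawal".

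The primary endpoint is the change in COWS from baseline to one hour, compared by a two-sided two-sample t-test with 25 subjects per arm (Primary Efficacy Variable; Power Calculation).

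**The concern.** The blind rests on patients being unable to tell a device with current from one without. A naive patient is told only that a sensation is possible and has nothing to compare it with. Someone who has worn an active device has that comparison. The cue comes at placement, before the one-hour assessment, so its fading after five minutes does not remove it.

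The Background and Rationale section lists subjective items in the COWS alongside objective signs. A patient who recognises the allocation could therefore shift the primary endpoint, most plausibly in favour of the active device. That direction is a reasonable expectation; the documents do not demonstrate it.

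The plan could not see the problem afterwards. Prior device use is not among the baseline items in Design and Methods, Baseline characteristics, Demographic Information or the visit schedule, which lists prior medications only. The allocation guess is collected once, at the end of treatment, and could not be split by prior exposure.

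Repeat entry is a secondary matter. If it happened, one person would count as two subjects in a test that treats subjects as independent.

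**Working it through.** **Step 1. Is the rule supplied anywhere else?**

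| Place | What it controls | Prior device use | Second randomisation |
|---|---|---|---|
| Inclusion paragraph | age, language, diagnosis, urine test, COWS, health | silent | silent |
| Exclusion criteria | illness, other substances, suicidality or homicidality, pregnancy | silent | silent |
| Subject recruitment and enrollment | study introduced at the initial clinic visit | silent | makes it less likely; not a criterion |
| Protection of privacy | one unique number per subject, linked to the name in a separate database | silent | would allow a check; none is stated |
| Data Points Requiring Special Handling | repeat assessments within a visit | silent | does not cover a repeat person |
| ITT and per-protocol definitions | all randomised; treated as randomised through the first hour | silent | a second entry would be kept in both |

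No section fills the gap.

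**Step 2. Which patients would know active stimulation?**

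- Patients who used the cleared device outside the trial: yes.
- Returning participants first randomised to active: yes.
- Returning sham participants who finished the five days and accepted the active device: yes. Only this group has felt both devices.
- Returning sham participants who left early or declined the offer: no, unless exposed elsewhere.

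**Step 3. The plan's own figures.** Inputs from Power Calculation: n = 25 per arm, difference 0.94 SD, two-sided alpha 0.049, SD about 6.

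- Noncentrality = 0.94 × √(25/2) = 3.32 on 48 degrees of freedom. Power is 90.1%, which agrees with the stated minimum of 90%.
- 0.94 × 6 = 5.64 COWS points, against the stated figure of about 5.7.

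**Step 4. Illustration only.** The documents give no rate of prior use or re-entry, so every input here is an assumption. Let f be the share of patients who recognise their allocation through earlier use, and b the resulting shift in the active-sham difference among them, in SD. Then overall bias = f × b, and in points f × b × 6. The type I error comes from a noncentral t with noncentrality f × b × √(25/2), at nominal 0.049. The SD is taken as unchanged and the interim look is ignored.

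| f | b | Bias (SD) | Bias (points) | Type I error |
|---|---|---|---|---|
| 4% | 0.5 | 0.02 | 0.12 | 0.0495 |
| 4% | 1.0 | 0.04 | 0.24 | 0.051 |
| 10% | 0.5 | 0.05 | 0.30 | 0.052 |
| 10% | 1.0 | 0.10 | 0.60 | 0.063 |
| 20% | 0.5 | 0.10 | 0.60 | 0.063 |
| 20% | 1.0 | 0.20 | 1.20 | 0.105 |

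For repeat entry, suppose k of the 50 randomisations were second entries and were set aside, leaving (50 − k)/2 per arm. Power at 0.94 SD would be 88.8% for k = 2, 86.7% for k = 5 and 82.3% for k = 10.

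**The case against.** Most of the case against a stronger version of this point stands.

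- **Repeat entry is improbable.** Recruitment takes place at the initial visit, at a single clinic, with one identifier per person, and the target is counted in subjects. The ordinary reading is one entry each. That reading is not written as a rule, but it makes broken independence in the t-test a remote prospect.
- **Early dropout does not produce patients who know both devices.** A reader might put the Day 5 offer beside the background remark that "up to 37.5 % of patients drop out of therapy within the first month and the majority of those occur during the first week" and infer a stream of returning patients who have felt both. The offer comes at the end of the five days and is optional, so a sham patient who leaves early never reaches it. The 37.5% is also a dropout figure from a cited study, not a rate of return to this clinic.
- **Prior outside use is only inferred.** FDA clearance makes it possible, but Study Purpose calls the device new and nothing shows that this clinic's patients have worn one.
- **Naive patients have a cue too.** They are told what they may feel, so excluding prior users leaves part of the unblinding risk in place. What it removes is the direct comparison from experience.
- **The endpoint has some protection.** The COWS includes objective signs, which the protocol says limit feigned answers, and it is rated by blinded staff.

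None of this supplies the missing rule, and the first two bullets do not touch patients exposed outside the trial.

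**Conclusion.** The point holds in a limited form. The criteria admit patients who have worn an active device before, and those patients are more likely than naive ones to recognise their allocation ahead of a partly subjective primary endpoint. This is the firmer half. The criteria also leave a second randomisation unprohibited. That is less likely, and only some returning participants would have had active exposure.

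The size is unknown. A reader might take the top of the illustrative range, 1.2 points or 21% of the detectable 5.7 (1.2/5.7), as an estimate of bias. The documents do not support that. It pairs 20% of patients recognising their allocation with a 6-point shift, which is itself larger than the detectable difference, and no section backs either input. At the bottom of the range the effect is negligible: 0.12 points, with type I error about 0.0495 against 0.049.

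This is a minor point, worth acting on because the remedy is cheap. It does not show that the primary comparison is biased.

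**What to change.** Add a sentence to Exclusion criteria, for example: *Patients who have ever worn a BRIDGE or another auricular nerve stimulator, or who have already been randomised in this study, are not eligible.* Support it with one screening question on past device use, and check the existing name-identifier link for earlier enrolment before randomisation.

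If the sponsor would rather not exclude prior users, the minimum is to bar a second randomisation, record past device exposure at baseline, and report the end-of-treatment allocation guess by that exposure. This makes the problem visible but does not prevent it.

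The cost is one sentence, one question and one look-up. A few patients with prior device use could not enrol, and the screening question relies on self-report for use outside the trial. The sample size and the analysis are unchanged.

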#### Subject recruitment and enrollment

Subjects presenting to the outpatient clinic at Brightview health will be identified by the attending physician and the patient will be approached for inclusion in the study by the research coordinator if they meet criteria. The principal investigator, a co-investigator or research coordinator will introduce the study to the patient during the initial clinic visit and will explain the details and purpose of the study during an informed consent discussion and obtain consent. Once the patient had enough time to consider participation, understand the risks and benefits and agree to participate, he/she will sign informed consent and HIPAA documents.

#### **Data Collected**

All data collected will be entered into a Redcap database for analysis. All collected data will be de-identified and samples will only have a unique identifier that will link the unique identifier with the patient's name.

Results of the COWS and pain VAS scores, OCS and CNSVS assessments at the respective time points will be tabulated and analyzed.

Upon completion of each patient's treatment with the device (sham or active), patients will be asked if they thought they had an active or inactive device. They will also be asked to respond to the questions: Do you want an active, functioning device to be placed prior to going home today (yes/no)? and on a 7 point Likert scale: 1) "How useful do you think the BRIDGE Device was for you overall in your treatment?" 2) "What is your impression of the effectiveness of the BRIDGE Device to treat your symptoms of withdrawal?" 3) "How satisfied are you and how the BRIDGE device worked for you?" and 4) "How likely are you to use the device again if you have symptoms of withdrawal?" Results will be tabulated and analyzed descriptively.

Analysis will also include differences in dosing of buprenorphine as well as usage of other symptom control medications and continued engagement in recovery treatment at 5- and 30-days post-device placement. If subject does not return to clinic at the 5- and 30-day scheduled appointment as dictated by clinic standard practice, a phone call will be made to assess whether the patient is still engaged in a recovery program.

### DATA MANAGEMENT

#### GENERAL CONSIDERATIONS FOR DATA ANALYSES

In general, for demographics, baseline disease characteristics, type of opioid misused, and all safety data, continuous variables will be summarized using descriptive statistics including N, mean, median, standard deviation (SD), minimum, and maximum. For all the efficacy parameters (e.g. COWS, VAS, OCS and CNSV experience with the device, continued engagement in recovery program) the descriptive statistics will include N, mean median, standard error (SE), minimum and maximum or percentage and exact Clopper Pearson 95% confidence interval.

**Definition of analysis population** Intent-to-treat (ITT) Population The intent-to-treat (ITT) population will include every subject who is randomized to a treatment assignment (BRIDGE or Sham). The ITT population will be the primary population for all efficacy analyses and will be the basis of all sensitivity analysis.

Patients who received study medication different from that to which they are randomized will be included in the group to which they are randomized. All data will be analyzed by randomized treatment group.

#### Per Protocol (PP) Population

The per-protocol population will be defined as the subset of the intent-to-treat population and will include patients who meet the following criteria:

• received BRIDGE or sham as randomized

• completed first hour of double-blind treatment

#### **Safety Population**

The safety population will consist of all patients who have received at least one hour of treatment. The safety population will be used for analysis of all safety data.

Patients who received study treatment different from that to which they were randomized will be included in the group according to the treatment actually used.

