
Overall, the study will have very little deviation from the current standard of practice to treat substance use disorder (SUD), with the exception of the first hour of medical management which will be effected without

buprenorphine or symptom control medications, and the second hour during which symptom control medications will not be used. Current standard of practice in the clinical setting is to give the first dose of buprenorphine on Day 1 after initial screening, followed by a second or third dose prior to discharge home. Patients will be sent home and monitored as outpatients and asked to return to clinic within 2-5 days. The current study will not deviate from clinical practice after Day 1 with the exception of having either the BRIDGE device or sham device for 5 days. The device will be removed at the clinic visit on Day 5 and disposed of in a sharps container. If the patient cannot come back on day 5, they will be instructed to remove the device at home and bring it back at the next clinic appointment for proper disposal.

#### Figure 3

If at any time the patient wishes to discontinue the BRIDGE device and receive standard treatment for opioid withdrawal outside the study, he/she will be allowed to do so.

The study will involve the use of the NSS-2 BRIDGE device, an ambulatory, neurological device which consists of a battery powered, externally affixed generator with 4 wire leads: 1 double needle electrode lead and 3 single point electrode needle leads (Figure 4). The device delivers low voltage (3.2V) stimulation in alternating frequencies for a total of 5 days (around the clock). The arrays are designed to produce a field effect. The leads will be placed percutaneously in the external ear with the help of a transilluminator to visualize the neurovascular bundles. Three electrodes will be placed on the ventral aspect and one on the dorsal aspect of the ear. The electrodes will be taped and secured behind the ear next to the generator itself which is secured to the skin with adhesive. The placement of the devices is within standard of care by properly trained medical providers or physician extenders.

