### Patient disposition and analysis population

The number of patients enrolled will be summarized by treatment group, and a patient listing of all patients excluded from each of the analysis populations will be generated.

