#### **REPORTING ADVERSE EVENTS AND UNANTICIPATED PROBLEMS**

All safety variables (e.g., adverse events will be summarized for each assessment time (including follow-up) using descriptive statistics. Incidence of adverse events will be summarized by treatment. Overall risks/ discomforts involved are very minimal – Rare (event rate 1% - < 5%)

Possible risks/discomforts may involve:

- Discomfort upon insertion of the electrodes for < 5 minutes Rare (event rate 1% < 5%)
- Discomfort at the lead placement site > 5 minutes Rare (1 % < 5%)
- Bleeding at the electrode site if the neurovascular bundle is penetrated Rare (event rate 1% <5%)
- Localized discomfort if the electrodes should become dislodged during the wearing of the device Rare (event rate 1% < 5%)
- Localized dermatitis Rare (event rate 1% < 5%)
- Drop in blood pressure Rare (event rate 1% < 5%)
- Syncope (fainting) Rare (event rate 1% < 5%)
- Adverse effects to supporting personnel
- Skin piercing with percutaneous needles Rare (event rate 1 % < 5%)

Of note, in the recently completed neurostimulation trial for functional abdominal pain disorders in adolescents, there were no serious adverse events. The rate of reported side effects was no different between the treatment and placebo groups. Of 115 subjects, n=10 (9%) reported the following side effects: ear discomfort (n=6; three treatment/three placebo), adhesive allergy (n=3; one treatment/two placebo) and syncope due to needle phobia (n=1; placebo) (18).

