#### **Safety Analysis**

The Bridge Device is FDA cleared as an aid in the treatment of opioid withdrawal symptoms. It has been classified as a class II device, with minimal no adverse effects in this population. Nevertheless, caution will be taken to monitor safety in this patient population. Safety assessments will consist of monitoring and reporting adverse events (AEs) and serious adverse events (SAEs) that are considered related to study device, all events of death, and any study specific issue of concern.

All safety variables will be summarized for each assessment time (including follow-up) by treatment group, and period using descriptive statistics. Incidence of AEs will be summarized based on body systems and preferred terms. Incidence of marked abnormal lab test results will be summarized. All safety summary outputs will be generated using the safety population.

This survey summary outputs will be generated using the sa

Exposure to Study Treatment

The following extent of exposure to study device will be summarized for each treatment group, and patient data listing will be produced:

- Overall adherence to assessment (i.e., average during the entire treatment period).
- Premature Withdrawals from the Protocol Therapy

• Patients (n,%) who prematurely withdraw from the protocol during the treatment period will be summarized separately for overall and by reason for withdrawal and will be presented in patient listing.

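### The safety population requires an hour of treatment, so an adverse event that ends treatment sooner is missing from the by-arm incidence tables

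*Combined protocol and SAP*

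**What the plan says.** The Safety Population section sets the entry rule: "The safety population will consist of all patients who have received at least one hour of treatment". It groups these patients by the treatment they actually used. The Safety Analysis section applies the set without exception: "All safety summary outputs will be generated using the safety population". The Adverse Events section defines incidence as the number of patients with at least one occurrence, divided by the number of patients in the stated population and arm.

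The Per Protocol (PP) Population section uses nearly the same condition: "completed first hour of double-blind treatment".

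Patients can leave before the hour is up. The first Data Management section covers a patient's own wish to stop ("If at any time the patient wishes to discontinue the BRIDGE device"), and the Safety Monitoring Plan covers harm: "If any serious harm or discomfort is identified by the subjects or the study personnel, the treatment will be discontinued". The section on reporting adverse events lists risks that can arise at placement, among them "Discomfort upon insertion of the electrodes for < 5 minutes", bleeding at an electrode site and syncope.

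The Adverse Events section also divides AEs into screening, treatment and follow-up periods that are summarized separately. The treatment period closes five days after the final day of device treatment. Follow-up takes new onsets that come more than 30 days after the most recent placement, plus certain events that began during treatment and persisted.

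**The concern.** A safety population normally takes in everyone exposed to the intervention, however briefly. Here, entry depends on getting through the first hour, so an AE that ends treatment in that hour also removes the patient from the table meant to count it. That hour includes needle insertion and the start of stimulation in the active arm. The tables would describe safety only in patients who completed it.

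What is at stake is the by-arm AE incidence. An early stop caused by an AE understates incidence in that arm. An early stop without an AE removes only a denominator count and raises incidence slightly. The net effect within an arm, and on the active-sham difference, can go either way.

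The lesser issue is that a reported event can fall between the treatment and follow-up periods and so appear in neither period-specific table.

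**Working it through.** The plan gives no figure for early stopping, so none can be reproduced. The check uses the population rule, the incidence formula and day counts.

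**Inputs.**
- 25 patients per arm (Power Calculation section).
- Listed event rates of 1% to less than 5% (section on reporting adverse events).
- Device worn for 5 days (first Data Management section).
- Period limits of 5 and 30 days (Adverse Events section).

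**Incidence.** In an arm of n, let x patients have the event. Let k of them stop within the hour, and let m others stop within the hour without an event. Incidence among all patients with a device placed is x/n. The plan's table shows (x − k)/(n − k − m). Intervals are exact (Clopper-Pearson) 95%. The documents do not give k or m, so the values below are assumptions that show a range.

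| Case (n = 25) | All with placement started | Under the plan's rule |
|---|---|---|
| x = 1, k = 1, m = 0 | 1/25 = 4.0% (0.1 to 20.4) | 0/24 = 0% (0 to 14.2) |
| x = 2, k = 2, m = 0 | 2/25 = 8.0% (1.0 to 26.0) | 0/23 = 0% (0 to 14.8) |
| x = 3, k = 3, m = 0 | 3/25 = 12.0% (2.5 to 31.2) | 0/22 = 0% (0 to 15.4) |
| x = 3, k = 1, m = 0 | 3/25 = 12.0% (2.5 to 31.2) | 2/24 = 8.3% (1.0 to 27.0) |
| x = 1, k = 0, m = 1 | 1/25 = 4.0% (0.1 to 20.4) | 1/24 = 4.2% (0.1 to 21.1) |

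At the plan's own rates, the expected number of patients with a given event in one arm runs from 25 × 0.01 = 0.25 to just under 25 × 0.05 = 1.25. Losing one patient can therefore empty a row. These are rates of having an event, not of stopping because of it.

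**Does any other text restore the patient?**
- The disposition section promises that "a patient listing of all patients excluded from each of the analysis populations will be generated".
- The Adverse Events section adds a listing of withdrawals due to AEs.
- The Serious Adverse Events section sends serious events in any enrolled subject to the IRB.
- The Safety Analysis section summarizes withdrawals by reason, but that summary may itself be limited to the safety population.

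None of these is an AE incidence table by arm.

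**AE periods.** Let T be the final device treatment day and P the day of the most recent placement. The treatment period covers onsets up to T + 5, and follow-up takes new onsets from P + 31. The uncovered days run from T + 6 to P + 30, which is P − T + 25 days.

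- Placement on Day 1, removal on Day 5: Days 11 to 31, or 1 − 5 + 25 = 21 days.
- Device stopped on Day 1: Days 7 to 31, 25 days.

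The section uses three anchors: the final treatment day, the most recent placement and the final dose day. It does not say whether the optional active device offered after Day 5 moves them. Across the readings worked through, the gap ran from 16 days (T = 10 on the optional device, P = 1) to 29 days (T = 1, P = 5 for the optional device). These are worked cases, not bounds. The second follow-up limb covers only events that began during treatment, so it does not fill the gap.

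**The case against.** The strongest objection is that few patients, perhaps none, will be affected. In the earlier adolescent neurostimulation trial that the protocol describes, 10 of 115 subjects (9%) had any side effect over the whole trial, and none is described as stopping. Three AE-related stops among 25 (12%) within an hour would exceed that total, so zero or one per arm is the more supportable illustration. The placement instructions also allow an uncomfortable array to be repositioned, so discomfort need not end treatment. The safety analysis is descriptive, and the listings and serious-event reports keep most such patients visible.

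Most of this stands, but it limits the size of the problem and leaves the rule as it is. Repositioning does not prevent a patient from leaving, and a listing does not supply the incidence that readers compare between arms.

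On the period gap, the objection has more force. The schedule ends at Day 5 and the 30-day contact is described only as a check on engagement, so few later events may be reported. The section on reporting adverse events also says, without limiting the period, "Incidence of adverse events will be summarized by treatment". The gap therefore affects only the period-specific tables and the events that happen to reach the investigators.

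A further objection concerns the remedy: a faint from needle phobia could precede the first insertion and still be missed by a rule based on insertion. That is a marginal case.

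**Conclusion.** The concern holds. As written, the safety population drops any patient who stops within the first hour, and no other provision returns that patient to the by-arm AE incidence tables. AEs in patients who continue past the hour are counted as intended.

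The realistic size is small in patients but large for a table row: one AE-related early stop changes 4.0% to 0% in an arm of 25. How often this will happen cannot be derived from the documents, and no direction of bias between arms can be claimed.

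The gap between AE periods is real, at 21 days for a patient who wears the device from Day 1 to Day 5. Its practical effect is minor, and the number of events involved is unknown. The plan should be corrected because the wording is clearly wrong and the repair costs little.

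**What to change.** In the Safety Population section, define the set as all patients in whom placement of a study device was started (any electrode inserted), whatever the duration of wear. Analyse them by the device actually used, or by the device dispensed if placement was not completed. This keeps the section's existing as-treated grouping.

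In the Adverse Events section:
- Tie all periods to one anchor on the randomized device.
- Start follow-up on the day after the treatment period ends, so that every reported onset falls in a period.
- Keep the limb for persisting events, using the same anchor.
- Tabulate events that start after placement of the optional active device separately from those on the randomized device.

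The cost is a few lines of SAP wording and slightly more tabulation. No patients or visits are added and clinical management does not change. Reported AE rates may look slightly less favourable. The change assigns reported events to a period but does not add AE collection after Day 5.
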